### **6.2.3.3. ANCOVA Analysis**

The ANCOVA analysis defined in section 6.2.2 will be repeated as a sensitivity analysis using the actual stratification factors in the model.

This sensitivity analysis will be performed on the mITT analysis set.

## **6.3. Secondary Efficacy Endpoints and Analysis**

The key secondary efficacy endpoint is the mean change in depression symptoms from randomization visit (day 1) to week 8 after the first dose of study drug as measured by HAM-D 17.

Other secondary endpoints include the following:

- Number of patients with 50% or more reduction from the 28-day baseline period until 12 weeks after the first dose of study drug, in the monthly average number of migraine days
- Mean change in quality of life from randomization visit (day 1) to week 12 after the first dose of study drug as measured by the MSQoL questionnaire, role function-restrictive, role function-preventive, and emotional function domains
- Mean change from randomization visit (day 1) in disability score for overall impact, as measured by CGI-S and HIT-6, to the following time points after administration of the first dose of study drug:
  - weeks 4 and 8 (CGI-S)
  - week 12 (CGI-S and HIT-6)

### **6.3.1. Hamilton Depression Rating Scale-17**

#### **6.3.1.1. Definition**

The HAM-D 17 ([Appendix C](#)) is a list of 17 items used to determine a patient’s level of depression. A total score of 0-7 is generally accepted to be within the normal range (or in clinical remission), while a score of 20 or higher (indicating at least moderate severity) is usually required for entry into a clinical trial.

#### **6.3.1.2. Analysis**

The HAM-D 17 total score change from baseline to week 8 will be analyzed using the same MMRM method as described in section 6.2.3.1. The analysis will also be done at weeks 4 and 12.

### **6.3.2. Migraine Days**

#### **6.3.2.1. Definition**

The 50% reduction in the monthly average number of migraine days during the 12-week period after the first dose of study drug will be calculated by formula 4 in section 6.1. If a patient is early discontinued from the study, they will be counted as not having a  $\geq 50\%$  reduction.

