## 2. STUDY DESIGN

### 2.1. General Design

This is an approximately 28-week, multicenter, randomized, double-blind, placebo investigational medicinal product (IMP)-controlled, parallel-group study to evaluate the efficacy and safety of fremanezumab self-administered at monthly doses of 225 mg sc and a quarterly dose of 675 mg sc (ie, one dose using 3 prefilled syringes with 225 mg each) in adult patients with migraine and MDD. The study will consist of a 28-day (ie, 4-week) baseline period, a 12-week double-blind treatment phase followed by a 12-week open-label extension phase, and an end-of-treatment visit (approximately 12 weeks after the final dose of study drug).

The total duration of patient participation in the study is planned to be approximately 28 weeks. Patients are expected to complete the entire duration of the study.

Patients who fulfill the criteria for migraine will be further delineated as patients with chronic migraine (CM) or episodic migraine (EM), for stratification and other analyses.

CM is defined as:

Patient fulfills the following criteria for CM in prospectively collected baseline information during the 28-day baseline period:

- headache occurring on  $\geq 15$  days
- on  $\geq 8$  days, fulfilling any 1 of the following:
  - ICHD-3 diagnostic criteria C and D for 1.1 Migraine without aura (Appendix I of the study protocol)
  - ICHD-3 criteria B and C for 1.2 Migraine with aura (Appendix I of the study protocol)
  - probable migraine (a migraine subtype where only 1 migraine criterion is missing)
  - triptan or ergot derivative used to treat established headache.

EM is defined as:

The patient fulfills the following criteria for EM in prospectively collected baseline information during the 28-day baseline period:

- headache occurring  $\geq 4$  days but  $< 15$
- on  $\geq 4$  days, fulfilling any 1 of the following:
  - ICHD-3 diagnostic criteria C and D for 1.1 Migraine without aura (Appendix I of the study protocol)
  - ICHD-3 criteria B and C for 1.2 Migraine with aura (Appendix I of the study protocol)

- probable migraine (a migraine subtype where only 1 migraine criterion is missing)
- triptan or ergot derivative used to treat an established headache

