At the randomization visit (day 1), patients will be randomly assigned to 1 of 2 treatment groups of 225 mg sc fremanezumab or placebo in a 1:1 ratio. Patients will receive their assigned study treatment on visit 2 (day 1), visit 3 (day 29), and visit 4 (day 57) and then continue into the open-label extension phase in which all patients will receive a quarterly dose of 675 mg sc fremanezumab on visit 5 (day 85). Investigators can contact patients in between study visits per their clinical judgment.

Patients who complete all scheduled visits will have procedures and assessments performed at visit 6 (end of treatment [EOT]). Patients who withdraw from the study before completing the 24-week treatment phase will have visit 6 (EOT) procedures and assessments performed at their final visit. The end of study is defined as the last visit (end-of-treatment/early withdrawal visit [visit 6]) of the last patient.

Study procedures and assessments with their timing are summarized in Table 4 of the study protocol.

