## **2.4. Sample Size and Power Considerations**

A sample size of 288 (144 per treatment group) evaluable patients completing the study will provide 90% power to detect a treatment difference of 2 days with a common standard deviation of 5.2 days in changes from the 28-day baseline period in monthly average migraine days between active and placebo groups at a 2-sided alpha level of 0.05. This sample size will provide approximately 80% power to detect a treatment difference of 2 points with a common standard deviation of 6 points in the change from randomization visit (day 1) in HAM-D 17 total score at a 2-sided alpha level of 0.05. Assuming a 15% drop-out rate, approximately 340 patients (approximately 170 patients per treatment group) will be randomized.

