### **2.5.2. Final Analyses and Reporting**

All analyses identified in this SAP will be performed after the final database lock.

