### **5.2. Patient Disposition**

Patients screened, patients screened but not randomized, and the reasons the patients were not randomized will be summarized only for the total group using patient counts.

Patients in the ITT analysis set, ITT analysis set but not treated, double-blind safety analysis set, double-blind mITT analysis set, double-blind mITT analysis set but not PP analysis set (with reason not in the PP set), and PP analysis set, patients who complete and withdraw from the double-blind treatment period, patients in the open-label safety analysis set and open-label mITT analysis set, and patients who complete and withdraw from the study will be summarized using descriptive statistics. Patients who withdraw from double-blind treatment and patients who withdraw from the study will also be summarized using descriptive statistics by reason for withdrawal. The denominator for calculating the percentages will be the number of patients in the ITT analysis set.

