## 7. MULTIPLE COMPARISONS AND MULTIPLICITY

A fixed-sequence (hierarchical) testing procedure will be implemented to control the type 1 error rate at 0.05. The primary endpoint will be tested first at a type I error rate of 5%. If the analysis is statistically significant (p-value <0.05), then the key secondary hypothesis will be tested. If not statistically significant, confirmatory hypothesis testing will not be carried out on the remaining hypotheses. This process will repeat accordingly to the order of the secondary endpoints as specified in section 6.3. [REDACTED]

[REDACTED]

[REDACTED]

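### As worded, the 12-week responder rule has no phase limit, so a week-12 responder who leaves during the open-label extension would be scored a non-responder

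*SAP*

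**What the plan says.** The responder endpoint, which concerns monthly migraine days, is listed in SAP section 6.3 as "Number of patients with 50% or more reduction from the 28-day baseline period until 12 weeks after the first dose of study drug". Section 6.3.2.1 calculates it by formula 4 over the 12-week period and then states the exception: "If a patient is early discontinued from the study, they will be counted as not having a" reduction of 50% or more.

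Four other places bear on what the study means in that sentence.

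- **SAP 2.1, composition:** "The study will consist of a 28-day (ie, 4-week) baseline period, a 12-week double-blind treatment phase followed by a 12-week open-label extension phase".
- **SAP 2.1, withdrawal:** it refers to "Patients who withdraw from the study before completing the 24-week treatment phase", so leaving in the open-label phase is withdrawal from the study.
- **SAP 5.2:** disposition counts "patients who complete and withdraw from the double-blind treatment period" separately from patients who complete and withdraw from the study.
- **SAP 2.5.2:** "All analyses identified in this SAP will be performed after the final database lock".

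On testing order, SAP section 7 starts with the primary endpoint, then the key secondary, and continues: "This process will repeat accordingly to the order of the secondary endpoints as specified in section 6.3". The responder endpoint is the first item listed there after the key secondary.

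**The concern.** The endpoint is a randomized comparison over 12 weeks. After week 12 every patient receives the same open-label drug. A rule that looks past week 12 makes the 12-week result depend on events after the comparison has ended, and it overrides diary data that were fully observed.

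This is a formally tested endpoint. If the primary and HAM-D 17 tests succeed and this one then fails, MSQoL, CGI-S and HIT-6 lose confirmatory testing. While the phase is unstated, two responder definitions fit the endpoint, and the choice between them could fall to programming.

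**Working it through.** **1. Reading the text.** SAP 2.1 and 5.2 give the study its whole-course meaning and list double-blind withdrawal as a separate category. SAP 8.2 likewise separates double-blind from open-label early withdrawal. SAP 3.1.4 limits the deviations that define the per-protocol set to the double-blind period, while SAP 5.9 summarizes deviations over the study. Narrower wording was therefore available and is not used in 6.3.2.1. Because analyses follow final lock, open-label withdrawals will be known when response is derived. Protocol section 9.5.4.3 has no discontinuation rule for responders, so it does not settle the meaning.

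**2. The plan's own figures.** These reproduce (two-sided 0.05, normal approximation).

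- Primary: n per arm = 2 × (1.960 + 1.282)² × 5.2² / 2² = 142.1, so 143 (plan: 144). Power at 144 is 90.4% (plan: 90%).
- HAM-D 17, difference 2, SD 6: 80.7% (plan: about 80%).
- Drop-out: "Assuming a 15% drop-out rate, approximately 340 patients (approximately 170 patients per treatment group) will be randomized". 288 / 0.85 = 339 and 144 / 0.85 = 170 per arm.

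The plan gives no power figure for the responder endpoint.

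**3. Size of the effect.** Response rates and the timing of drop-out are not in the documents, so these are assumptions:

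- response p of 40% versus 25%, with 170 per arm;
- the plan's 15% total drop-out, equal in both arms;
- a share OL of each arm leaving in the open-label phase, and db = 0.15 − OL leaving earlier;
- earlier leaving unrelated to response;
- in the open-label phase, non-responders leaving k times as often as responders.

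Formulas:

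- Rate with the rule limited to week 12: p(1 − db).
- Rate as written: p(1 − db) − OL × p / [p + k(1 − p)].
- Recoded responders: 170 × OL × the sum over arms of p / [p + k(1 − p)].
- Power: Φ[(difference − 1.96 × SE0) / SE1], with SE0 pooled and SE1 unpooled.

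Worked case, OL = 5%, k = 1:

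- Limited to week 12: rates 0.360 and 0.225; (0.135 − 1.96 × 0.0493) / 0.0488 = 0.78; power 78.4%.
- As written: rates 0.340 and 0.2125; (0.1275 − 1.96 × 0.0485) / 0.0480 = 0.68; power 75.0%.

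| OL | k | Power, limited to week 12 | Power, as written | Responders recoded, both arms | Loss, points |
|---|---|---|---|---|---|
| 2% | 1 | 76.4% | 75.0% | 2.2 | 1.4 |
| 2% | 3 | 76.4% | 75.6% | 1.0 | 0.8 |
| 3% | 1 | 77.1% | 75.0% | 3.3 | 2.0 |
| 3% | 3 | 77.1% | 75.9% | 1.4 | 1.2 |
| 5% | 1 | 78.4% | 75.0% | 5.5 | 3.3 |
| 5% | 2 | 78.4% | 75.9% | 3.3 | 2.5 |
| 5% | 3 | 78.4% | 76.4% | 2.4 | 2.0 |
| 10% | 1 | 81.4% | 75.0% | 11.1 | 6.4 |
| 10% | 2 | 81.4% | 76.7% | 6.7 | 4.8 |
| 10% | 3 | 81.4% | 77.8% | 4.8 | 3.7 |

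Other assumed rates at OL 5-10%, k from 1 to 3: 35% versus 20% loses 1.6 to 5.6 points, and 45% versus 30% loses 2.3 to 7.1. The analysis set is mITT, so n may be below 170; at an assumed 160 per arm and 40% versus 25%, the loss is 2.0 to 6.6. The test is an unadjusted approximation to the planned logistic regression.

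**4. Unequal leaving.** Take 12-week rates of 45% versus 30% (OR 1.91), ignoring double-blind drop-out. If 10% of active and 5% of placebo responders leave later, the rates become 40.5% and 28.5% (OR 1.71). With the shares reversed they are 42.75% and 27.0% (OR 2.02).

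**5. Place in the sequence.** This test is confirmatory only after two successes. If those were independent (an assumption), the chance is 0.904 × 0.807 = 0.73. Losses of 2.0 to 6.4 points then become about 1.4 to 4.7 points of confirmatory success.

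**The case against.** The strongest reply is that the authors meant double-blind discontinuation. The disputed sentence follows directly on one that fixes the 12-week window, and its evident purpose is to deal with patients who lack a full 12-week outcome. The SAP uses similar unqualified shorthand where only the double-blind period can be meant: early termination in the MMRM and multiple-imputation sections, and early discontinuation in the primary estimand. The SAP contents also list an Appendix B on the logic of endpoint derivation. It is not in the available text and may cover this flag.

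Most of this stands. It makes the narrow intent plausible and limits the claim to the visible wording. It does not remove the problem. In the MMRM and imputation sections the values concern months 1 to 3, so later withdrawal cannot change them; in 6.3.2.1 it changes the outcome.

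It is also fair that nothing in the documents makes 5% open-label leaving a floor. That phase has one dosing visit and one later visit, and at 2-3% the loss is only 0.8 to 2.0 points.

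A reader might infer that the rule favours fremanezumab or inflates type I error. The documents do not support that. With equal leaving unrelated to arm, both rates fall and the difference shrinks. With unequal leaving the odds ratio can move either way, and the documents give no basis for a direction.

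**Conclusion.** The point holds as a defect of wording in a formally tested endpoint, with moderate confidence. Read literally, SAP 6.3.2.1 recodes genuine 12-week responders who leave in the open-label phase. On the stated assumptions the cost is about 1 to 2 points of power at 2-3% open-label leaving and about 2 to 6 points at 5-10%.

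Two stronger conclusions might be drawn and should not be. One is that the sponsor intends to penalize open-label leavers; the context leans the other way, and Appendix B is unseen. The other is that the trial's main conclusions are at risk. The primary and key secondary endpoints do not use this rule, and the consequence for later secondary endpoints arises only if both of those succeed first. Lines after the visible part of SAP section 7 are redacted, so the full testing procedure cannot be confirmed.

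**What to change.** In SAP 6.3.2.1, keep discontinuation from the study as the trigger and add a time limit directly after it: *before week 12 (during the double-blind treatment period)*. Patients who complete the 12 weeks are then classified by formula 4 whatever happens in the open-label phase. If Appendix B covers this flag, apply the same limit there.

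The trigger should not be changed to discontinuation of double-blind treatment. Protocol section 4.3 distinguishes stopping study drug from leaving the study. That substitution could newly fail a patient who stops injections but stays in the study and keeps the diary to week 12.

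The cost is a few words. No new data are needed, because SAP 5.2 already summarizes withdrawal from the double-blind period. The change should be made before unblinding.

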### **6.3.2.2. Analysis**

For the proportion of patients with  $\geq 50\%$  reduction, a logistic regression model will be used with the following effects: treatment, sex, region, migraine classification, and baseline PHQ-9 score category. The stratification factors (as randomized) will be used in the model. The odds ratios (fremanezumab vs. placebo), 95% CI for the odds ratio, and associated p-value will be generated from this model.

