9.5.4.3. Secondary Efficacy Analysis

The continuous secondary efficacy endpoints will be analyzed similarly as the primary efficacy endpoint. Analyses using the mixed-effect model repeated measure method will be conducted for continuous variables assessed at multiple time points. For the proportion of responders, defined as 50% or more reduction from the 28-day baseline period in the monthly average number of migraine days, a logistic regression model will be used with the following effects: treatment, sex, region (United States, European, or rest of world), migraine classification (ie, CM or EM), and baseline PHQ-9 score category. The ORs, 95% confidence intervals (for ORs), and p-values will be presented for fremanezumab comparing to placebo.

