The **percentage of reduction** in the monthly average number of an efficacy variable will be calculated as

$$\frac{\text{baseline value} - \text{postbaseline value}}{\text{baseline value}} \times 100\% \quad (4)$$

where the baseline value is calculated by formula (3) and the postbaseline value in the equation is calculated by formula (1) for the variables *during the 12-week period* or by formula (2) for the variables *during the 4-week period* after each dose for months 1, 2, 3, and 6.

The mITT analysis sets will be used for all efficacy analyses. Summaries will be presented by treatment group as randomized, unless otherwise noted. For the double-blind treatment period, summaries will be presented by treatment group. For the open-label treatment period, summaries will be presented by double-blind treatment group and all patients (ie, total). Descriptive statistics for all efficacy data will be presented by month (or week), and over 12-week period for the double-blind period, and at month 6 (or week 24) for the open-label treatment period. For migraine days and PHQ-9 total score, months 1, 2, and 3 (or weeks 4, 8, and 12) will also be included in the open-label treatment period summaries.

The primary and secondary endpoints analysis listed in section 6.2.1 and section 6.3 will be repeated for the PP analysis set.

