### 6.2.2. Primary Efficacy Analysis

The hypothesis testing for the primary analysis is:

$$H_o : \delta_1 = \delta_2 \quad vs \quad H_a : \delta_1 \neq \delta_2$$

where  $\delta_1$  and  $\delta_2$  are the mean change from baseline in the monthly average number of migraine days for the fremanezumab treatment group and the placebo treatment group respectively.

The primary efficacy endpoint will be analyzed using an analysis of covariance (ANCOVA) model with sex, region (United States, European, or rest of world), migraine classification (ie, CM or EM), baseline PHQ-9 score category (10 to 14, 15 to 19, and  $\geq 20$ ), and treatment as factors and baseline number of migraine days as a covariate. The stratification factors (as randomized) will be used in the model. The least square (LS) mean treatment difference (fremanezumab - placebo), 95% confidence interval (CI) for the LS mean treatment difference, and the associated p-value will be generated from this model.

The statistical test will be two-sided at the alpha=0.05 level of significance. The SAS code for this test is as follows:

```
PROC MIXED;
  CLASS TREAT SEX REGION MIGCLASS PHQCAT;
  MODEL CHG= TREAT SEX REGION MIGCLASS PHQCAT BASE;
  LSMEANS TREAT / DIFF CL;
RUN;
```

The normality assumption for the ANCOVA model will be checked to ensure validity of the primary analysis. If the model assumptions are not met (p-value <0.01), a nonparametric method such as Wilcoxon Rank Sum test will be conducted as a sensitivity analysis.

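### The 50%-responder logistic model omits baseline migraine days, which the primary model fits alongside CM/EM; no reason is given, and the cost is probably small

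*SAP*

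**What the plan says.** SAP 6.3.2.2 specifies that "a logistic regression model will be used with the following effects: treatment, sex, region, migraine classification, and baseline PHQ-9 score category", using the strata as randomized. Protocol 9.5.4.3 gives the same list, so the two documents agree.

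The primary ANCOVA in SAP 6.2.2 uses the same strata but ends with "treatment as factors and baseline number of migraine days as a covariate". The MMRM in SAP 6.2.3.1, which is reused for HAM-D 17, MSQoL, CGI-S and HIT-6, also carries the baseline value. For PHQ-9, SAP 6.4.1.2 says expressly that the baseline value is left out of the model. SAP 6.3.2.2 has no such remark.

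The percentage reduction (SAP 6.1, formula 4) is the fall in migraine days divided by the baseline value. On dropouts, SAP 6.3.2.1 says "If a patient is early discontinued from the study, they will be counted as not having a" reduction of at least 50%.

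On testing order, SAP 7 says "This process will repeat accordingly to the order of the secondary endpoints as specified in section 6.3". The responder endpoint is listed there first after HAM-D 17. SAP 2.4 and protocol 9.1 state no power or responder rate for it.

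**The concern.** Among the primary and listed secondary endpoints, this is the only model that does not adjust for the endpoint's own baseline. The primary model fits both CM/EM and baseline days, so the plan itself does not treat the first as a replacement for the second.

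If baseline days predict response within a class, leaving them out wastes precision that is already available, and a chance imbalance between arms can move the odds ratio. The position in the sequence raises the stake: under the readable text of SAP 7, a non-significant responder test stops confirmatory testing of MSQoL, CGI-S and HIT-6.

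**Working it through.** **1. The plan's own figures (SAP 2.4).** Power = Φ(δ / (σ√(2/n)) − 1.96) with n = 144 per arm.
- Migraine days: 2 / (5.2 × 0.1179) = 3.26, so power = Φ(1.30) = 90.4% (stated: 90%).
- HAM-D 17: 2 / (6 × 0.1179) = 2.83, so power = Φ(0.87) = 80.7% (stated: about 80%).
- Randomized: 288 / 0.85 = 339 (stated: about 340).

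These reproduce. There is no stated responder figure to check.

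**2. What CM/EM leaves unadjusted.** The definitions (SAP 2.1) allow 4 to 14 migraine days in EM and 8 to 28 in CM. Response requires losing half of baseline, so 2 to 7 days in EM and 4 to 14 in CM. These are limits set by the definitions; the documents give no baseline distribution. Assuming half the patients have CM, with baseline means of 9 (EM) and 17 (CM) and SDs of 2.7 and 4.5 truncated to the class limits, CM/EM explains about 56% of the variance in baseline days.

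**3. When baseline matters.** Response means reduction ≥ baseline / 2. If the expected reduction is proportional to baseline, the division cancels it and baseline predicts little. If the reduction in days hardly depends on baseline, patients with high counts respond less often and baseline is prognostic.

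**4. Power without and with baseline days.** N = 340, allocation balanced within CM/EM, 2000 trials per row, all SAP 6.3.2.2 effects fitted, Wald test at two-sided 0.05. Assumed responder rates are about 21–26% (placebo) and 33–37% (active). Compare within rows only.

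| Assumed within-class odds ratio per SD of baseline | Without | With |
|---|---|---|
| 1.0 | 74.9% | 75.0% |
| 1.25 | 72.4% | 73.3% |
| 1.5 | 72.6% | 73.6% |
| 2.0 | 66.5% | 69.7% |
| 3.0 | 60.2% | 68.4% |

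Other ways of generating response:
- Through formula 4 with the plan's 2-day effect and SD 5.2, and an assumed placebo reduction of 10–40% of baseline: gain 0.0 to 0.4 points (for example 72.2% to 72.5%).
- With a purely proportional effect: −0.4 to +0.1 points.
- With 144 per arm, a 2-day effect and the baseline–change correlation r varied (1000 trials per setting; class and PHQ-9 category only): about 3 points at r = −0.07 (82.0% to 85.1%; 67.3% to 70.3%), 0–1 at −0.25, none at −0.40 or stronger.
- With 340 randomized and 15% dropouts counted as non-responders: about 2 points when reduction hardly depends on baseline, 1 or less at r = −0.15 to −0.35, none at −0.44.

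The simulation standard error of a single power near 72% with 2000 trials is √(0.72 × 0.28 / 2000) = 1.0 point. The two models share data, so differences are more precise than that, but gains below 1 point should not be read closely.

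**5. Type I error.** 4.3–5.3% without and 4.5–5.8% with the covariate (simulation error about 0.5 points).

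**6. Chance imbalance.** With 170 per arm, two standard errors of the difference in mean baseline are 2 × √(2/170) = 0.22 SD. The unadjusted odds ratio then shifts by a factor of about (odds ratio per SD)^0.22: 1.05 at 1.25, 1.09 at 1.5, 1.16 at 2.0 and 1.27 at 3.0.

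**The case against.** Adjusting a binary endpoint for the randomization factors alone is coherent, and both documents prespecify it. CM/EM is stratified and fitted, so much of the baseline severity is already accounted for. The test is confirmatory only if the primary (90% power) and HAM-D 17 (about 80%) succeed first. Adding the covariate also changes what is estimated: at an assumed odds ratio of 2.0 per SD, the treatment odds ratio moves from 1.82 to 1.93, with a larger standard error. All of this stands. It lowers the priority but does not explain why this endpoint alone leaves its baseline out.

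A reader might infer three stronger things that the documents do not support:
- That power must be lost because baseline is the denominator. Dividing by baseline already removes much of the dependence, so being the denominator does not make it prognostic.
- That any baseline imbalance passes straight into the odds ratio. It does so only in proportion to the prognostic strength left within class.
- That the result would be biased or invalid. Randomization protects on average, and the simulated type I error is intact. The 1.82 and 1.93 above are less and more conditional odds ratios, not a wrong and a right one.

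**Conclusion.** The omission is real, prespecified in both documents and unexplained, and it affects a test in the fixed sequence. It is a minor loss of efficiency at most. A realistic expectation is a gain of about 0 to 3 points of power from adding the term. The 8-point gain and the 1.27 imbalance factor both require an odds ratio of 3 per SD within class, which nothing in the documents suggests. The worst change seen was −0.4 points, within simulation error.

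Every responder power figure here rests on assumed responder rates, CM share, baseline distributions and prognostic strength; the plan supplies only the 2-day effect, the SD of 5.2, the sample size and the dropout rate.

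**What to change.** Before unblinding, add baseline number of migraine days (continuous) to the responder logistic model in SAP 6.3.2.2 and protocol 9.5.4.3. Report the present model as a sensitivity analysis. If the sponsor prefers the present model, one sentence giving the reason would settle the point.

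The cost is one model term on data already collected. The downside is an odds ratio conditional on one covariate more than the four already in the model; the sensitivity analysis shows how far that moves it.
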